1.1 Theoretical framework

This study will examine sleep-related beliefs and behaviors in the context of the Social Cognitive Theory (SCT; Bandura, 1986). Self-efficacy is perhaps the most well-established construct in the SCT and was an important predictor of sleep quality in our pilot work (Brooks et al., *Under Review*). We anticipate that the SHUTi program will directly impact personal, environmental, and behavioral factors for participants, and the theory includes all three as potential predictors of outcomes (insomnia severity and ultimately relapse).

1.2 Study Objectives:

1. *Phase I:* Assess the feasibility and acceptability of Internet-based CBT-I among individuals with AUD in recovery
2. *Phase II:* Compare the efficacy of CBT-I versus an education-only control group with respect to primary and secondary outcome variables
 - a. Primary outcome variables include: changes in insomnia severity over time, changes in actigraphy-recorded sleep efficiency over time
 - b. Secondary outcome variables include actigraphy-related (objective) variables, alcohol consumed (post-discharge), alcohol craving (post-discharge), sleep disturbance, daytime sleepiness, anxiety/depression, fatigue, self-efficacy for sleep, dysfunctional beliefs about sleep, and functional outcomes
 - c. Explore specific domains associated with improved outcomes: e.g. demographic, psychiatric, and/or drinking-related factors

2 Study design and methods

This is a two-phase study. Phase I will be focused on assessing feasibility and effectiveness of program delivery and data collection (n=10). Phase II will be a pilot RCT powered to examine intervention

Protocol Number: 18-CC-0079

effectiveness in the target population (n=20 per group). All study participants will receive a handheld tablet to access the SHUTi or education-only program.

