Insomnia Severity Index (ISI). The ISI is a seven-item global index of self-reported insomnia symptom severity. It is valid, reliable, sensitive to changes in insomnia treatment (Bastien, Vallieres, & Morin, 2001; Morin, Belleville, Belanger, & Ivers, 2011) and validated for online use (Thorndike et al., 2011). Seyffert and colleagues (2016) categorized insomnia severity by scores as follows: 0-7 = no clinically significant insomnia, 8-14 = subthreshold insomnia, 15-21 = moderate insomnia, and 22-28 = severe insomnia. Changes in the ISI over time will be a primary outcome measure. The ISI is collected within the SHUTi intervention program at the beginning of each core, but participants in both Phase I and Phase II will also complete a paper version of the ISI during the pre-, mid-point, and post-test assessments.

Daily sleep and symptom diaries. Prospectively collected sleep diaries are a proven method for assessing insomnia and track treatment effects (Carney, et al., 2012; Buysse, Ancoli-Israel, Edinger, Lichstein, & Morin, 2006) and have been used for other sleep studies among patients on 1SE (inpatient and outpatient). Participants will be asked to complete at least five out of every seven days of daily sleep and symptom diaries. These diaries will include sleep/wake times, time in bed, sleep onset latency, number and duration of awakenings, sleep quality, naps, alcohol consumption, any over-the-counter or prescription medications used to help with sleep (participants will be instructed to include any marijuana use in this section), and open-ended comments. For the experimental group, diaries will be used to assess adherence to their “sleep window,” based on actual time in bed as a proportion of prescribed time in bed. We will cross-validate diary-reported sleep duration with actigraphy data when possible. Secondary outcome measures captured in the diaries will include a categorical measure of relapse (i.e. whether the participant reports any drinking post-discharge) as well as quantity and frequency of drinking, which will be calculated in the case of relapse, as well as all other diary variables.

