Objective measure of sleep: actigraphy. "Actiwatches" are small wristband data loggers that record digitally-integrated measures of gross motor activity. These devices contain accelerometers and light sensors in order to objectively assess sleep. Prior studies have demonstrated actigraphy's high sensitivity with moderate accuracy for detecting sleep in populations with normal and disturbed sleep when compared to polysomnography (Kushida et al., 2001; Paquet et al., 2007). The *Actiwatch Spectrum Plus* (Philips Respironics) has been used in previous studies with patients on 1SE in both inpatient and outpatient settings. The watch is worn on the non-dominant wrist. Study participants will be asked to wear an actiwatch for 4 days, 3 nights (Phase I only) and for at least 1 week (Phase II only) at three study time points (Pre SHUT-i®/Education-Only initiation, 3-4 weeks after SHUT-i®/Education-Only initiation and Post SHUT-i®/Education-Only program completion). Participants will return the actiwatches either in person (if the participant will be returning to the Clinical Center) or by mail after each study time point so that the research team can download the data and return the watch to the participant (with the exception of the last study time point). The main outcome of interest will be improvements in sleep efficiency from baseline to follow-up assessment periods. The watch also provides measures of total sleep time (TST), wake after sleep onset (WASO), sleep onset latency (SOL), number of awakenings (NWAK), and time in bed (TIB).

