Any experimental pharmacological agent may affect the data collected for this study and its effect on sleep will be largely unknown. As a result, our research team decided on excluding participants that are enrolled in any experimental pharmacological study.

PI Name: [name]

Version Date: 12/07/2020

Protocol Number: 18-CC-0079

Study measures have only been validated in English.

Additional note: after enrollment in the study, the management of sedatives/hypnotics for individuals who have been prescribed either will be done by a clinician who is blind to the treatment condition.

Protocol Number: 18-CC-0079

3 Statistical analysis:

Qualitative analysis (Phase I participants only). Each audio-recorded interview will be transcribed verbatim. A codebook will be developed based on themes from the interviews. Each code will be accompanied by an operational definition that will allow for clarity and consistency in the coding process. Evidence of each code or theme will be assessed using quotes from the interviews. A team of coders will independently review all transcripts. Discordant coding will be discussed until consensus among the coding team is achieved. Once the iterative process of consensus building is complete, an intramural expert in qualitative methodology will validate the final themes and coding. After data are coded, NVivo will be utilized for further qualitative analysis and data management.

Quantitative analyses (Phase II only). The first step in quantitative data analysis will be running baseline "diagnostics" to check for outliers and normal distribution of all continuous variables. If the assumptions of normality are not violated, we will proceed with parametric testing. If the assumptions of normality are violated, non-parametric tests will be utilized. For quantitative analyses, statistical significance will be considered at $p < 0.05$.

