Phase II: 60 participants - the total sample size for phase II of this study will test the primary hypotheses associated with the analysis plan. With insomnia severity as the primary outcome, we will use a two-sided alternative hypothesis that the rate of change will be different between the intervention group and the control group. Assuming a correlation of 0.6 between the two time points, an alpha level of 0.05, a power level of 0.8, and an estimated attrition rate of 40 percent, we will be able to detect an effect size of 0.84 with 60 participants (Fitzmaurice, Laird, & Ware, 2012). Permuted block randomization with block size of four will be used to equally assign participants in each group. The statistician, who will not have any contact with participants, will prepare the randomization sequences and give out the allocation assignment after each participant is consented.

Mixed model for repeated measure with group, time, and the interaction of group by time will be used to test the changes of insomnia severity in two groups. Mixed model for repeated measures will also be used to test the secondary objectives with potential covariates in the model. Demographic, psychiatric, and/or drinking-related factors significantly related to the outcomes listed in the secondary objectives will be entered in the model. Aikake information criterion and the Bayesian information criterion will be used to select best-fitting models. A potential dosing effect analysis including the number of cores completed as a covariate will be conducted for the treatment group only. With the linear mixed model approach, all available data points will be included in the analyses. Under missing completely at random and missing at random assumptions, linear mixed model with restricted maximum likelihood estimation can produce unbiased estimators (Salim, Mackinnon et al. 2008).

Investigator Conflicts: NIH guidelines on conflict of interest have been distributed to all investigators. NIH guidelines on conflict of interest have been distributed to all investigators.

Technology Transfer: No technology transfer agreement is in place for this protocol.

4 Rationale for subject selection

This study will be open to both males and females of all racial and ethnic groups, without targeting any specific group. We anticipate the target enrollment of participants to reflect the racial/ethnic distribution of residents in the greater Washington DC metropolitan area.

5 Recruitment plan

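### Section 2.4 adds all remaining diary variables to the secondary outcomes and Section 3 calls every test at p < 0.05: with about 25 tests and no true effect, the chance of at least one false difference is 47–72%, and of a false benefit 23–47%

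*Combined protocol and SAP*

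**What the plan says.** Section 1.2, objective 2, is to compare the efficacy of the programme with the education-only control on primary and secondary outcomes. Item 2b begins "Secondary outcome variables include actigraphy-related (objective) variables" and goes on to drinking and craving after discharge, sleep disturbance, sleepiness, anxiety/depression, fatigue, self-efficacy, beliefs about sleep and functional outcomes. No diary sleep variable appears there. Only item 2c, on domains associated with improvement, is worded as exploratory.

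Section 2.4, in the actigraphy paragraph, gives the watch variables other than sleep efficiency: "total sleep time (TST), wake after sleep onset (WASO), sleep onset latency (SOL), number of awakenings (NWAK), and time in bed (TIB". The diary paragraph names as secondary "a categorical measure of relapse (i.e. whether the participant reports any drinking post-discharge) as well as quantity and frequency of drinking", and then adds "as well as all other diary variables".

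Section 3 sets one threshold: "For quantitative analyses, statistical significance will be considered at" p < 0.05. It tests the secondary objectives with mixed models for repeated measures. The power statement concerns insomnia severity. No section gives a testing order, a key secondary outcome, a multiplicity adjustment or a descriptive label for secondary p-values.

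**The concern.** Two things combine. The set of secondary outcomes is wider in Section 2.4 than in Section 1.2, and its last part is defined by reference to whatever the diary holds. Each member is then tested at the same threshold as the primary outcome. Because the stated objective is an efficacy comparison on secondary outcomes, a significant result on any of them could be reported as planned evidence that the programme works. With this many tests, such a result can arise by chance far more often than the nominal 5% suggests, and nothing in the plan tells the reader to discount it.

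**Working it through.** **The plan's own figure.** Section 3 states a detectable effect of 0.84 with 60 participants, using a correlation of 0.6, alpha 0.05, power 0.8 and 40% attrition. Completers per arm: 30 × (1 − 0.4) = 18. Variance of a change score in SD units: 2 × (1 − 0.6) = 0.8. Detectable effect: (1.960 + 0.842) × √(2 × 0.8 / 18) = 0.835. At 0.84 the normal-approximation power is 0.804. The figure reproduces, for a single test of insomnia severity. The documents state no familywise error rate and no count of secondary tests.

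**Counting the secondary tests.**
- Five watch variables (Section 2.4, actigraphy).
- Three drinking outcomes: relapse, quantity, frequency (Section 2.4, diaries).
- Nine questionnaires: PACS, FOSQ-10, PSQI, MFSI-SF, ESS, SE-S, DBAS-16, IDS, Trait Anxiety.
- Subtotal: 5 + 3 + 9 = 17.
- Other diary items: sleep and wake times, time in bed, onset latency, number of awakenings, their duration, sleep quality, naps, sleep medication. That is 8, or 9 if sleep and wake times are counted separately.
- Total: 25 or 26, taken as about 25.

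Item 2b read alone gives about 15: the five watch variables and ten others, with alcohol consumed counted once.

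**Chance of a false finding.** Assume no true effect on any outcome, one two-sided 0.05 test per outcome, and m tests. Section 3 states a two-sided hypothesis for insomnia severity; the same is assumed here for the secondary outcomes. With independent tests:
- either direction: 1 − 0.95^m. For m = 25, 1 − 0.95^25 = 0.723.
- benefit only: 1 − 0.975^m. For m = 25, 1 − 0.975^25 = 0.469.

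With a common correlation between test statistics (normal, one-factor numerical integration; the values 0.3 and 0.5 are assumptions):

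| Tests | Direction | Independent | Correlation 0.3 | Correlation 0.5 |
|---|---|---|---|---|
| 17 | either | 58% | 49% | 39% |
| 17 | benefit | 35% | 25% | 19% |
| 25 | either | 72% | 61% | 47% |
| 25 | benefit | 47% | 32% | 23% |

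For 25 tests the either-direction figure drops below one half at a correlation of about 0.46. Under independence the benefit figure passes one half only at 28 tests (0.508). At 28 tests and a correlation of 0.3 it is 34%.

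**Effect of a Holm adjustment.** With 15 outcomes the first step is 0.05/15 = 0.0033, critical value 2.935. Detectable effect: (2.935 + 0.842) × √(1.6 / 18) = 1.13 SD, against 0.84 unadjusted. With 17 outcomes the threshold is 0.05/17 = 0.0029 and the detectable effect is 1.14 SD.

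**The case against.** A reader might infer that a chance benefit is more likely than not, or that a useless programme would usually show a significant secondary result. The documents do not support either statement. The 72% counts differences in both directions, harm included, and assumes independence. The chance of a false benefit is below one half at 25 tests even under independence. Independence is also implausible: diary and watch both record onset latency, awakenings and time in bed in the same people, and Section 2.4 plans to cross-validate diary sleep duration against actigraphy. This part of the objection stands, and it is why the correlated figures are given equal place.

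Some variables are not clean efficacy tests. Time in bed is prescribed by the sleep-restriction component, so a difference there would reflect adherence. Drinking quantity and frequency are calculated only where there is relapse. These points make the count approximate; they do not remove the problem.

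It may also be said that the diary clause is not truly open, since the same paragraph lists the diary's contents, and that item 2b only says what its list includes. That is largely fair: Section 2.4 extends Section 1.2 and does not contradict it. What remains undefined is how each item is summarised and whether derived variables, such as diary sleep efficiency, count.

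Finally, this is called a pilot, and strict familywise control over secondary outcomes in 60 people costs a good deal of power. That stands against requiring Holm. It does not answer the absence of any label: the protocol also describes Phase II as powered for effectiveness, and places the secondary outcomes under an efficacy comparison.

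**Conclusion.** The concern holds in this form: the secondary family is about 25 tests, partly undefined, each judged at p < 0.05, with no order, adjustment or descriptive status. Under no true effect, the chance of at least one significant difference is 72%, 61% or 47% at correlations of 0, 0.3 or 0.5, and of at least one false benefit 47%, 32% or 23%. A single two-sided test allows 2.5% in the benefit direction, so the inflation is roughly 9-fold (23.4/2.5) to 19-fold (46.9/2.5).

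These sizes rest on the count above, on one test per outcome, on two-sided testing of the secondary outcomes, and on assumed correlations. Separate contrasts at mid-point and post-test would enlarge the family. The primary comparison of insomnia severity is not affected by this point. The figures do not show that a spurious benefit is the expected outcome; they show that one is far too likely for an unadjusted p < 0.05 to support an efficacy claim.

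**What to change.** 1. In Section 1.2, make the secondary list closed. Name the five actigraphy variables and the drinking variables, including relapse, and make Section 2.4 refer back to that list.
2. In Section 2.4, move the remaining diary variables to exploratory, and state how each will be summarised.
3. In Section 3, restrict the p < 0.05 significance rule accordingly: report secondary and exploratory results as estimates with 95% confidence intervals and, at most, nominal p-values, and state that no efficacy claim will be drawn from an unadjusted p < 0.05.
4. A Holm adjustment across the closed list is optional, for use if the sponsor wants confirmatory secondary claims. It raises the detectable effect at the first step to about 1.13 SD with 15 outcomes.

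The cost is protocol wording, with no added participants, visits or data. The downside is that fewer secondary results can be called significant.

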Penn Alcohol Craving Scale (PACS). The PACS is a clinical tool for practitioners to measure alcohol craving. It is a five-item self-administered instrument that measures frequency, intensity, and duration of thoughts about drinking along with ability to resist drinking. The final item asks the responder to provide an average rating of his or her craving over the course of the past week. The PACS has excellent internal consistency (Cronbach's $\alpha = 0.92$). Construct, predictive, and discriminant validity has also been established. This assessment takes between two and five minutes to complete (Flannery, Volpicelli, & Pettinati, 1999). The PACS will be administered as part of the post-test assessment.

Functional Outcomes of Sleep Questionnaire (FOSQ-10). The FOSQ-10 is a 10-item abbreviated version of the original 30 item instrument used to evaluate quality of life in relation to daytime sleepiness. The 30-

Protocol Number: 18-CC-0079

item questionnaire measures difficulty in performing tasks from five domains due to sleepiness or tiredness: General Productivity, Activity Level, Vigilance, Social Outcome, and Intimacy and Sexual Relationships (Weaver et al., 1997). The FOSQ-10 consists of two questions from General Productivity subscale, three from Activity Level, three from Vigilance, and one each from Social Outcome and the Intimacy and Sexual Relationships subscales. The 10-item version demonstrates high internal consistency similar to that of the original instrument (Cronbach's $\alpha = 0.87$), high correlation with the 30-item version of the scale, and the ability to detect a wide range of functional limitations (Chasens, Kampman, & Weaver, 2009). To obtain the total score for the FOSQ-10, the mean-weighted item score is calculated for each subscale. These subscale scores are then averaged and the mean was multiplied by five. Lower scores are indicative of higher levels of dysfunction. The FOSQ-10 will be administered at pre- and post-test time points.

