Composite Scale of Morningness (CSM). The Composite Scale of Morningness is a 13-item scale (Smith, Reilly, & Midkiff 1989). Questions address topics like morning affect, preferred sleep/wake times, and peak cognitive performance, with scores ranging from 13 (reflecting "eveningness") to 55 (reflecting "morningness"). The CSM typically shows relatively high internal consistency (Cronbach's alpha > 0.8) (Di Milia, Adan, Natale, & Randler 2013).

We will pull additional data from the screening/treatment protocol to characterize our sample and conduct exploratory analysis based on the aforementioned aims, including but not limited to:

- Childhood Trauma Questionnaire (CTQ)
- Structured Clinical Interview for Diagnostic and Statistical Manual of Mental Disorders (DSM-IV or DSM-5) (SCID)
- Clinical Institute Withdrawal Assessment – Alcohol revised (CIWA-Ar)
- Comprehensive Psychopathological Rating Scale (CPRS)

[figure not shown]

Figure 1: Study flow chart

Participants will be screened for eligibility on or after day 14 of inpatient treatment. Days 14-21 will be when the participant is consented, screened for OSA (after consent), randomized (if they meet inclusion requirements), and begin daily diary assessments as a baseline measure. If they are discharged before they are deemed eligible for continue study participation and randomized to a group, they will be removed from the study.

Table of Measures						
	Inpatient			Outpatient		
	Pre-Test (Before SHUT-i® Intervention or Education only program initiation)	Start SHUT-i® Intervention or Education only program	Prior to or within 2 weeks of Discharge	3-4 weeks after SHUT-i® Intervention or Education only program initiation	Post-Test (After SHUT-i® Intervention or Education only program completion)	6-7 months post-discharge (clinic visit or by phone)
ISI				X		X
PACS					X	X
PSQI	X			X	X	
DBAS-16	X				X	
FOSQ-10	X				X	
SE-S	X				X	
IDS	X				X	
ESS	X				X	
Trait Anxiety Inventory	X				X	
CSM	X					
MFSI-SF	X				X	
At least 4 days, 3 nights (Phase I)/1 week (Phase II) of actigraphy assessment	X			X	X	
Sleep Diaries	X			X	X	
Start SHUTi (Phase I and II) or education only (Phase II only) program		X				
Abbreviated Internet Evaluation and Utility Questionnaire (Phase I only)			X			

Protocol Number: 18-CC-0079

Internet Impact and Effectiveness Questionnaire, Internet Evaluation and Utility Questionnaire, and the Internet Intervention Adherence Questionnaire (Phase I and II)					X	

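### Craving (PACS) has no pre-test measure and no named test; the group-by-time term, if carried over from insomnia severity, would not measure the effect of SHUTi on craving

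*Combined protocol and SAP*

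**What the plan says.** Section 1.2 lists craving among the secondary outcomes, next to drinking: "alcohol consumed (post-discharge), alcohol craving (post-discharge".

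On timing, the PACS paragraph in Section 2.4 reads "The PACS will be administered as part of the post-test assessment" and names no other visit. The next paragraph shows how the authors write a baseline when they plan one: "The FOSQ-10 will be administered at pre- and post-test time points". The Table of Measures marks PACS in two columns, "Post-Test (After SHUT-i® Intervention or Education only program completion)" and "6-7 months post-discharge (clinic visit or by phone)", and leaves its pre-test cell empty. PSQI, DBAS-16, FOSQ-10, SE-S, IDS, ESS, trait anxiety and MFSI-SF all carry a pre-test mark. So text and table agree that there is no pre-test PACS, and disagree on whether there is one at 6-7 months.

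On analysis, Section 3 (Phase II) sets the insomnia hypothesis as one of change: "we will use a two-sided alternative hypothesis that the rate of change will be different between the intervention group and the control group". Its model is "Mixed model for repeated measure with group, time, and the interaction of group by time will be used to test the changes of insomnia severity". For the rest it says: "Mixed model for repeated measures will also be used to test the secondary objectives with potential covariates in the model". No term, visit or contrast is named for craving.

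**The concern.** A repeated-measures model needs at least two visits, and its group-by-time term has the meaning of a treatment effect only when one of those visits precedes treatment. Neither condition is secured for PACS.

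- On the Section 2.4 text there is one visit, so no time or interaction term exists.
- On the table there are two visits, both after the program. Group-by-time is then the arm difference in change from end of program to 6-7 months. A benefit that is present at post-test and maintained contributes nothing to it.

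At stake is whether the trial can say anything clear about craving. If the interaction is used by analogy with insomnia severity, a sustained benefit is missed and a lost benefit can look like a finding. If the choice among group term, interaction and single-visit contrast is left open, it may be made after the data are seen. The absent baseline also rules out a change analysis and a check of baseline balance in craving. With 40% attrition planned for, a participant lost before post-test contributes no PACS value at all, which weakens the missing-at-random argument in Section 3 for this outcome.

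**Working it through.** **Inputs from Section 3:** 60 participants, 40% attrition, equal allocation, correlation 0.6, two-sided alpha 0.05, power 0.8, detectable effect 0.84 SD. These are planning values for insomnia severity. The documents give none for PACS, so 0.84 SD and 0.6 are assumptions here.

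**The plan's own figure.**
- Completers: 60 × (1 − 0.40) = 36, or 18 per arm.
- SD of a change score: √(2 × (1 − 0.6)) = 0.894.
- Detectable difference: (1.960 + 0.842) × √(2 × 0.8 / 18) = 0.835, against 0.84 stated.

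The figure reproduces, and nothing here disputes it.

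**Group-by-time with PACS at post-test and 6-7 months.** Let b1 and b2 be the benefit at the two visits, in SD units. The interaction estimates b2 − b1, with standard error 0.894 × √(2/18) = 0.298 (between-visit correlation 0.6). The post-test arm difference estimates b1, with standard error √(2/18) = 0.333. The average over both visits estimates (b1 + b2)/2, with SD √((1 + 0.6)/2) = 0.894. Rejection rates from 40,000 simulated trials, 18 per arm, t-tests:

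| Benefit at post-test, at 6-7 months | Size of b2 − b1 | Group-by-time | Post-test difference | Average group effect |
|---|---|---|---|---|
| 0.84, 0.84 | 0 | 4.8% | 69% | 78% |
| 0.84, 0.42 | 0.42 | 28% | 68% | 53% |
| 0.84, 0 | 0.84 | 78% | 69% | 28% |

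In the first row the interaction rejects at its type I error rate. In the third it rejects often because the benefit has gone.

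**What a pre-test PACS would add.** With a covariate correlated r with the outcome, the residual SD is √(1 − r²). Power is for a 0.84 SD effect at post-test, t-based and checked by simulation. The detectable effect is the normal approximation 2.802 × √(2(1 − r²)/18).

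| Pre-post correlation r | Residual SD | Power | Detectable at 80% power |
|---|---|---|---|
| no baseline | 1.000 | 69% | 0.93 SD |
| 0.3 | 0.954 | 72% | 0.89 SD |
| 0.5 | 0.866 | 80% | 0.81 SD |
| 0.6 | 0.800 | 85% | 0.75 SD |
| 0.8 | 0.600 | 98% | 0.56 SD |

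**The later visit.** Section 2.2 lets education-only participants request the full SHUTi program from three months after discharge. The 6-7 month PACS falls after that, so its arm contrast may be diluted.

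**The case against.** The strongest reply is that the plan never assigns the interaction to craving. Group, time and group-by-time are written out for insomnia severity only; for the secondary objectives the same class of model is said to be used also, with covariates. That model contains a group effect, which is a randomised comparison and needs no baseline. In the equal-benefit case above, the average group effect has 78% power. This stands: a reader might infer that the craving test as written has no power, but the documents do not go that far. They leave the test unnamed.

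Second, Section 1.2 labels craving post-discharge, whereas the primary outcomes are changes over time, and the pre-test takes place during inpatient treatment. Post-only collection may be deliberate. This also stands: the documents do not show the missing baseline to be an oversight. It does not rescue the interaction, and a pre-test value used as a covariate would leave the outcome post-discharge.

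Third, a reader might infer that lacking a baseline biases the comparison. It does not; randomisation protects the post-test contrast under complete follow-up, and chance imbalance costs precision. Section 3 also allows drinking-related and psychiatric covariates, and Section 2.4 draws open-endedly on the parent protocol, although no craving scale is among the data listed.

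Fourth, the 5% needs exactly equal benefit at both visits, and the gain from a baseline is small if inpatient and post-discharge craving correlate weakly. Both are fair, which is why ranges are shown.

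Last, the table is weak evidence alone: as read here, its insomnia row lacks the pre- and post-test marks that Section 2.4 requires. The PACS paragraph supports the absence of a pre-test independently.

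**Conclusion.** The point holds in limited form. Text and table give no pre-test PACS and disagree on the 6-7 month visit, and Section 3 names no test for craving beyond the repeated-measures model. If group-by-time is carried over, it is inestimable with one visit. With two, it tests post-program drift, with about 5% power against a benefit equal at both visits, about 28% if the benefit halves, and about 78% if it vanishes.

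A valid test is available without any baseline: the arm difference at post-test, at about 69% power for 0.84 SD. A baseline raises that to between 72% and 98% over correlations of 0.3 to 0.8. These figures assume 18 completers per arm and borrow the insomnia effect size, so they show the size of the issue and do not predict PACS results. Craving is one of many secondary outcomes in a pilot, and the primary analysis is unaffected.

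**What to change.** 1. In Section 3, name the arm difference in PACS at post-test as the test for craving, and say that it is not group-by-time. This costs one sentence and should be settled before the data are examined.
2. Add the five-item PACS to the existing pre-test battery and use it as a covariate. Section 2.4 puts the scale at two to five minutes, at a visit already scheduled. People already enrolled would lack the value, so state how they stay in the analysis. If enrolment is too far on for this to be useful, item 1 alone is sufficient.
3. Make the PACS paragraph in Section 2.4 and the Table of Measures agree on the 6-7 month visit. If that visit is kept, treat it as supportive, and report how many control participants took up SHUTi before it.
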